Human Oral Microbe Identification using Next Generation Sequencing (HOMINGS) utilizes the speed and efficiency of next generation sequencing combined with the refinement of species-level identification. Nearly 600 oral bacterial taxa are identified at the Species-level and Genus-level identification of remaining sequences for 129 genera. HOMINGS allows identification and comparison of bacterial associations in oral health and disease, including different types of periodontitis, caries, gingivitis, ventilator-associated pneumonia, endodontic and odontogenic lesions, abscesses, and halitosis. Also, HOMINGS can determine the efficacy of therapies/treatments, e.g., mouth rinses, antibiotic treatment, scaling and root planning, and laser or periodontal surgery. HOMINGS will be utilized for microbial analysis in this study.

Research Question:

What is the mechanism of action of silver diamine fluoride (SDF) on bacteria involved in root or cervical carious lesions using human oral microbe identification microarray (HOMINGS) technology?

Objective:

To **assess** the effect of SDF treatment on a large array of microorganisms present in root or cervical carious lesions using HOMINGS technology. This will be accomplished by assessing microbial deposits on root or cervical caries lesions before and 1 month after SDF application.

Rationale:

Older people that have caries-active disease experience root caries at a rate which is at least as great as that of coronal caries among adolescents.²⁷

The use of fluoride releasing agents as a means of preventing dental caries has long been recognized, and amongst these agents silver diamine fluoride (SDF) has received considerable attention as a caries-arresting agent of choice.²⁸

Silver diamine fluoride outperforms other anticaries medicaments such as chlorhexine, NaOCl-based gel (Carisolv), and an enzyme-based gel (Papacarie) in killing cariogenic bacteria in dentinal tubules, and results in less aversive taste and texture responses than to fluoride varnish.²⁹

38% SDF arrests dental caries producing bacteria such as *Streptococcus mutans*, *Streptococcus sobrinus*, *Lactobacillus acidophilus*, *Lactobacillus rhamnosus* and *Actinomyces naeslundii* by reducing the demineralization process. It minimizes the loss of mineral content and slows down collagen I

destruction. Furthermore, it contains high concentrations of silver and fluoride ions, which may inhibit the growth of multi-species cariogenic biofilms.¹⁰

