Safety is an important aspect, which should be considered in the clinical use of SDF solution. An important review considered silver diamine fluoride (SDF) as a safe, effective, efficient, and equitable caries-preventive agent that appears to meet the criteria of the WHO Millennium Goals and the US Institute.^{28, 30} The effect of SDF in preventing dentine collagen degradation from bacterial collagenase challenge has also been well documented.³¹ The germicidal action of the SDF preparation in arresting active caries and contributing to disinfection of root canals has also been documented.³²

There are 3 components of SDF: silver, amine, and fluoride. Silver alone and the more complex silver nitrate have been used for millennia for medical applications. Fluoride is now widely used in a multitude of applications for caries prevention. Unlike the application of fluoride among children, the use of higher concentrations of fluoride among the elderly is acceptable and cannot cause fluorosis.³³

Hypothesis:

H₀: there is no inhibitory effect of bacteria by 38% SDF

H_A: there is an inhibitory effect of bacteria by 38% SDF

Materials and Methods:

Setting: General Dentistry clinics of the University of Michigan School of Dentistry.

Approval from the Internal Review Board Med (IRB) of the University of Michigan will be obtained prior to implementation.

Study Subjects and Screening:

Inclusion Criteria:

- Generally healthy adult participants 18 years of age and older.
- At least one tooth with active (soft) cavitated lesions of ICDAS score 5 or 6 near the gingival margin (coronal cervical caries at the CEJ or exposed root surfaces with soft active carious lesions exposing dentin).

Exclusion Criteria:

- Adult participants who suffer from serious life-threatening medical diseases that interfere with basic daily self care activities.
- Patients taking antibiotics within the last two weeks.
- Patients using chlorhexidine or fluoride mouth washes within the last two weeks.
- Pregnant or breastfeeding women.
- Teeth with arrested (hard) cervical or root caries lesions.
- Teeth that have been diagnosed with an abscess or an irreversible pulpitis, or are mobile.

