- 2/Examination and diagnosis for root or cervical surface caries to confirm if caries still exist (Photographs when possible)

3/Bacterial sample collection

Outcome Measures and its Assessment:

Patients will be seen twice, at baseline and at one-month recall, to compare the microbial composition of bacterial samples at the two different stages. Also, questionnaires will be completed by the patients at baseline and after one month to collect information on tooth brushing behavior, use of fluoride toothpaste, frequency of sweet snack intake between meals. Patients will also be asked about the acceptability of the treatment. Two eligible subjects with multiple eligible lesions will be seen for plaque collection calibration to ensure the plaque sample technique yields adequate volume to extract bacterial DNA for analysis. These subjects can also participate in the baseline and one-month recall, if the subject elects.

Incentives:

1/Participants will be given a toothbrush and toothpaste at the initial visit, and \$10 for their initial participation. We will pay for patient parking for the visit.

2/Fifteen dollars at the one-month recall research clinical visit. We will pay for patient parking at the visit.

3/At the one month recall, if active caries still exists or if the patient does not like the color, patients will be offered an appropriate restoration at our expense at the General Dentistry Clinic at the University of Michigan.

4/Two subjects will also participate in a test plaque sample collection visit. These subjects will receive \$18 for this visit and will receive compensation for patient parking.

Collection and determination of the bacteria involved in the carious lesions:

Gracey curettes will be used to collect plaque samples. Plaque samples will be coded, which will allow the samples to be connected to the overall study data. These samples will be used to identify the types of bacteria involved in the carious lesions and bacteria arrested after the application of the testing material after one month. The microbial composition of the samples will be assessed using human oral microbe identification microarray (HOMINGS). After the bacterial collection, the samples from the cervical or root carious lesions will be suspended in tubes containing 150 µl of TE (Tris, EDTA) Buffer. The bacterial samples will be stored at -80 °C. Prior to shipment to Forsyth for HOMINGS analyses, genomic DNA will be

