purified using the Master Pure Gram Positive DNA Purification kit (Epicentre Biotechnologies, Madison, WI, USA), with modifications (<http://mim.forsyth.org>). DNA samples will be sent on dry ice to Forsyth Institute. Per Forsyth Institute and the University of Michigan Office of Technology Transfer, a Material Transfer Agreement (MTA) will not be required prior to sharing of the samples.

HOMINGS:

At the Forsyth Institute, microbial profiles will be generated from image files of scanned HOMINGS microarrays (<https://homings.forsyth.org>). In brief, concentration levels of approximately 600 oral taxa will be determined by microarray hybridization using a fluorescent readout reverse-capture method.³⁶

Fluorescently labeled sample microbial DNA will be captured by 16S rRNA-based probes attached to glass slides. The fluorescent intensity for each probe will be scanned, normalized and scaled as previously reported.³⁶ Signals of 2× backgrounds will be considered to be negative and assigned a HOMINGS level score of 0. Positive hybridization signals will be categorized into five levels, with 1 indicating a signal that was just detectable, and 5 indicating maximum signal intensity.³⁷

Statistical Analysis:

Data will be analyzed using SPSS Pc+ version 22.0 statistical software. Descriptive statistics (mean, standard deviation, frequencies and percentages) will be used to describe the quantitative and categorical variables. Appropriate parametric statistical tests (one way analysis of variance followed by Tukey's test) and non-parametric statistical tests (Pearson's chi-square and Krushal Wallis test) will be used depending on the type and distribution of variables. A p-value ≤ 0.05 will be used to report the statistical significance of results.

Future Research:

Data and any samples remaining following HOMINGS analysis may be retained for future analysis/research. Subjects will provide or deny permission for their samples and data from this project to be used in future research in the informed consent document.

References:

1. Petersen PE, Yamamoto T: Improving the oral health of older people: the approach of the WHO global oral health programme. *Community Dent Oral Epidemiol* 2005; 33:81–92.

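### The stated outcome is microbial composition at two visits, but no whole-community comparison is specified: the named tests are univariate, assigned to no outcome, and would run over about 600 taxa

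*Combined protocol and SAP*

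**What the plan says.** The section on outcome measures gives the purpose of the two visits as "to compare the microbial composition of bacterial samples at the two different stages". The Objective is to study "the effect of SDF treatment on a large array of microorganisms present in root or cervical carious lesions using HOMINGS technology". The alternative hypothesis is that "there is an inhibitory effect of bacteria by 38% SDF".

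The HOMINGS section describes the data: "concentration levels of approximately 600 oral taxa will be determined by microarray hybridization". Each taxon is scored 0 when negative; otherwise, "Positive hybridization signals will be categorized into five levels, with 1 indicating a signal that was just detectable, and 5 indicating maximum signal intensity". A sample is thus a profile of about 600 scores from 0 to 5.

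The Statistical Analysis section lists descriptive statistics, one-way ANOVA followed by Tukey's test, Pearson's chi-square and Kruskal-Wallis. The tests "will be used depending on the type and distribution of variables", with significance at p ≤ 0.05. It mentions no between-sample distance, diversity index, count of taxa detected or whole-profile test, and no adjustment for multiplicity. No test is linked to a named outcome.

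**The concern.** The outcome is a property of the whole sample, while every named test takes one response variable. Following the plan produces up to about 600 separate taxon results, with no rule for combining them into an answer on composition or into a decision on the null hypothesis, which concerns bacteria in general.

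This gap is distinct from two others in the same section: the named tests treat the visits as independent groups although each patient supplies both samples, and multiplicity is not controlled. Repairing both would leave a cleaner list of taxa but still no test of whether the profile as a whole moved. What is at stake is the main conclusion. A few significant taxa could be reported as a change in composition when that many would be expected by chance.

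**Working it through.** **Inputs from the documents.** 20 subjects, each sampled at two visits (Sample Size); about 600 taxa scored 0–5 (HOMINGS); a 0.05 threshold per test (Statistical Analysis). The sample size comes with no power, effect size, SD or dropout allowance, so there is no plan figure to reproduce.

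**Step 1: taxon tests at 0.05 when nothing changes.** Expected false positives = m × 0.05. Chance of at least one, for independent taxa = 1 − 0.95^m.

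- m = 600: 30 expected; chance essentially 100%.
- m = 100: 5 expected; 1 − 0.95^100 = 99.4%.

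Correlation between taxa lowers the chance only a little: with 100 taxa and paired tests, simulated null trials gave at least one significant taxon in 94–99%. With 600 independent taxa scored 0–5 and the planned Kruskal-Wallis test, all of 200 null trials did. The mean number significant was 28.3 at within-patient correlation 0 and 7.2 at 0.5; the second is lower because the test ignores pairing.

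**Step 2: the same tests when there is an effect.** Two assumed scenarios with 20 pairs and 100 taxa: 30% of taxa falling by 0.4 SD of the paired difference, or 50% falling by 0.3 SD. Unadjusted paired tests gave at least one significant taxon in 100% of 400 trials, about 15 on average. Having some significant taxa is thus nearly certain with or without an effect.

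**Step 3: adjusted taxon tests against one whole-profile test.** Let d_ij be recall minus baseline for patient i and taxon j. The statistic is T = Σ_j (mean over i of d_ij)², the squared Euclidean distance between the mean profiles. Swapping visit labels in a patient reverses the sign of that patient's whole row. There are 2^20 = 1,048,576 such patterns, so the smallest two-sided p is 2/2^20 ≈ 1.9 × 10⁻⁶ and the test is feasible with 20 patients.

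The table shows 100 taxa with normal differences, taxa standardised, and a single shared factor with random sign. Entries are the chance of at least one discovery with false-discovery control at 5%, against rejection by the whole-profile test; ranges are over three separate runs.

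| Assumed shift | Correlation 0.1 | Correlation 0.3 |
|---|---|---|
| 30% of taxa, 0.4 SD | 58–62% v 97% | 53–56% v 40–44% |
| 50% of taxa, 0.3 SD | 40–45% v 95–98% | 35–39% v 40–43% |

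With no effect the whole-profile test rejected in about 4–7%.

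**Step 4: the 0–5 scale.** With 600 independent taxa scored 0–5 and 30% shifted by 0.3 SD up or down, the whole-profile test rejected in 95% (within-patient correlation 0) and 100% (0.5) of 200 trials. Kruskal-Wallis with Bonferroni (0.05/600 = 8.3 × 10⁻⁵) found any taxon in 6% and 0%. Null rejection of the whole-profile test was 4.5% and 6.0%.

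**Step 5: choice of scale.** When every taxon is halved, proportions do not change. Bray-Curtis distance on proportions then rejected in only 2.5–4% of trials, against 100% for Euclidean distance on an absolute (log) scale.

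**The case against.** The strongest reply is that the documents never define composition as a community-level quantity. The sample-collection section says "These samples will be used to identify the types of bacteria involved in the carious lesions and bacteria arrested after the application"; the Objective and the hypothesis can also be read organism by organism. On that reading, taxon results with descriptive tables by visit are a composition comparison. A univariate test could also be applied to a summary such as the number of taxa detected. Much of this stands. A reader might infer that the composition comparison is never made, or that the trial does not test its own outcome; the documents do not support that, because a partial comparison is there. What remains is that no summary is named, no test is assigned, and nothing says how the taxon results combine.

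A reader might also infer that a broad, modest effect would probably be reported as no effect. That is wrong for the plan as written: without adjustment, some taxon is significant in practically every trial. The danger is false positives. Missed effects arise only once adjustment is added, and then only in some of the settings above.

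Finally, the whole-profile test has no direction, whereas the alternative hypothesis is inhibition, and its advantage disappears or reverses when taxa are more strongly correlated. Taxa scraped from one lesion with one curette may well be. Both points stand and shape the fix.

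**Conclusion.** The point holds in this form: composition at two visits is the stated outcome, no whole-community comparison is specified, and the taxon list that the plan would produce cannot show whether the community changed. That last part is firm, since it follows from about 600 tests at 0.05 and from the 94–99% null figure with 100 taxa.

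The size of any power gain is not firm. The number of detectable taxa, share affected, effect size and correlations are all assumptions; the documents give only the approximate taxon count and the number of patients. The gain runs from large (about 97% v 60%) to negative (about 40% v 55%) as between-taxon correlation goes from 0.1 to 0.3. The case for the test is therefore that it gives one valid answer to the stated question, not that it is always more powerful. It should be added before analysis. It would show a change between visits; with no control group it would not attribute that change to SDF.

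**What to change.** In the Statistical Analysis section:

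1. Name one test of the composition outcome: Euclidean distance between the mean baseline and mean recall profiles on the HOMINGS 0–5 levels, with the p-value from swapping visit labels within each patient. If taxa are rescaled, the scaling must be unaffected by the swaps or recomputed for each one.
2. Do not use proportions as the main scale, because they cancel a uniform fall. If the laboratory delivers sequence counts, as the Introduction's description of HOMINGS suggests, state the absolute scale to be used before analysis.
3. Report with it the within-patient change in number of taxa detected, with a 95% interval, to supply the direction that the test lacks.
4. Use paired, multiplicity-adjusted taxon tests to show which taxa changed and in which direction, not as the test of composition.

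The cost is a short paragraph, one more result to report and a brief permutation script, possibly outside SPSS. No new data or patients are needed.

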Generally healthy adult participants 18 years of age and older with at least one tooth with active cavitated lesions of ICDAS score 5 or 6 near the gingival margin (coronal cervical caries at the CEJ or exposed root surfaces with soft active carious lesions exposing dentin) will be recruited by one of the researchers after the IRB approval in the General Dentistry Clinic at the University of Michigan. Other providers in the General Dentistry Clinic, or other departments, will be informed of the eligibility criteria by the study PI personally, via word of mouth, and via study flyers or emails, and can refer potential subjects to the study team. This could occur either at a patient appointment, or via a review of the patient chart (please see request for Waiver of Consent). The PI will approach potential subjects in person or via phone call to assess interest in study participation. If interested, a study appointment will be scheduled and Informed Consent performed.

At the study appointment, patients will be provided with verbal and written information describing the purpose of the study and potential side effects (lesions will turn black). They will be informed that all information is confidential and that they can freely withdraw at any time during their participation. They will have the opportunity to ask questions related to the study. After obtaining written informed consent, study subjects will be examined by the study PI. Status of the cervical or root caries lesions will be assessed by visual inspection and aided by tactile detection using a probe. Decay- missing- filled teeth (DMFT) index will be assessed for each patient at the initial visit. We will also use ICDAS sensitivity and specificity criteria scores 5 and 6. Score 5 is a distinct cavity with visible dentin; frank cavitation involving less than half of a tooth surface. Score 6 is an extensive distinct cavity with dentin; cavity is deep and wide involving more than half of a tooth surface.

Food particles obscuring visual inspection of root or cervical surfaces will be removed. Two surfaces per tooth (buccal and lingual) will be examined clinically for root surface caries. Individualized oral hygiene instructions will be provided to each participant, focusing on effective brushing with a manual toothbrush, and use of fluoride toothpaste will be recommended.

[figure not shown]
Treatment:

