Eligible study subjects will have plaque collected from 1 randomly selected caries lesion that meets the inclusion criteria. Before applications of the study agent, a piece of gauze will be used to dry the teeth. Bacterial samples from subjects' root or cervical carious lesions will be collected with sterile Gracey curettes via a gentle scraping movement.^{34,35} Samples will be collected at the beginning of each appointment, but following consent and eligibility review. Samples will be frozen until analyses. The SDF solution will then be applied onto the exposed root surfaces of participants by means of a disposable microbrush following the manufacturer's recommendation by using their specialized Advantage Arrest applicator. The applicator will not absorb the product as it applies, and there is no risk of leaving flock portions of the applicator on the site. The surface tension of the material being applied holds the liquid on the applicator until it contacts the application site. The participants will be instructed not to eat or drink for one hour after treatment. Patients will be asked to return 1 month later. At this time, the lesions will be assessed for changes in hardness and color, and then a second microbial sample will be collected as described below and frozen until analyses.

Sample Size:

A sample including 20 subjects is decided to constitute the study sample. Samples will be collected from each patient at the first visit and at the one month recall visit.

An additional 2 test plaque samples will be collected for calibration purposes. These will be collected either from subjects who will also participate in the main project or 2 additional subjects. Plaque sampling on the two test subjects will be for calibration purposes, to ensure the sampling technique yields samples with sufficient volume to reliably extract bacterial DNA.

Patient Participation:

Test Sample Collection (2 subjects):

- 1/Consent form and Eligibility review
- 2/Questionnaire
- 3/Examination and diagnosis for root surface caries (photographs when possible)
- 4/Bacterial sample collection

1st appointment:

- 1/Consent form and Eligibility review
- 2/Questionnaire
- 3/Examination and diagnosis for root surface caries (Pre-SDF photographs when possible)
- 4/Bacterial sample collection
- 5/SDF application
- 6/Post-SDF application photograph

2nd appointment (one month recall):

- 1/Questionnaire

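### The laboratory outcome is described as two different assays, and the comparison of two visits in the same subjects is assigned only independent-group tests

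*Combined protocol and SAP*

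**What the plan says.** **Assay.** The Introduction describes the method this way: "Human Oral Microbe Identification using Next Generation Sequencing (HOMINGS) utilizes the speed and efficiency of next generation sequencing". The same paragraph ends by committing to it: "HOMINGS will be utilized for microbial analysis in this study". The Research Question, shortly afterwards, speaks of "using human oral microbe identification microarray (HOMINGS) technology". The section on collecting and identifying the bacteria also calls it a microarray. The HOMINGS section gives the working detail: "microbial profiles will be generated from image files of scanned HOMINGS microarrays", from probes on glass slides. Fluorescence is normalized and scaled by reference to a cited paper. Negative signals score 0 and positive signals score 1 to 5. No other laboratory variable is defined.

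**Comparison.** Treatment, Sample Size and Outcome Measures describe 20 subjects, one sampled lesion each, with samples at baseline and at one month. Statistical Analysis names one-way ANOVA with Tukey's test, Pearson's chi-square and Kruskal-Wallis, at p ≤ 0.05.

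**Hypothesis and sampling.** The alternative hypothesis is that "there is an inhibitory effect of bacteria by 38% SDF". Outcome Measures, by contrast, speaks of comparing microbial composition. Samples "will be collected with sterile Gracey curettes via a gentle scraping movement". The two calibration samples check only that the volume is enough for DNA extraction. Under Study Subjects and Screening, "Individualized oral hygiene instructions will be provided to each participant". At recall, under Treatment, "the lesions will be assessed for changes in hardness and color, and then a second microbial sample will be collected".

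**The concern.** There are two errors as written, and one smaller gap.

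1. Sequencing yields read counts; a hybridization array yields fluorescence. The two need different outcome variables, different handling of zeros and different normalization. If the laboratory runs sequencing, the plan has no defined laboratory outcome. If it runs the array, the Introduction describes the wrong method.
2. The central comparison is within subject. A test that treats 20 baseline and 20 recall samples as 40 independent observations leaves between-subject variation in the error term. With only 20 pairs, the loss of power matters.
3. The hypothesis is about inhibition, but the signal may also depend on how much plaque was on the curette. If the amount differs between visits, a lower score need not mean fewer bacteria on the lesion.

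**Working it through.** **Step 1: the assay descriptions side by side.**

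| Place | Assay | Output |
|---|---|---|
| Introduction, HOMINGS paragraph | Next-generation sequencing | Nearly 600 taxa at species level; remaining sequences assigned to 129 genera |
| Research Question | Microarray | None stated |
| Collection and determination of the bacteria | Microarray | Composition |
| HOMINGS | Microarray, scanned slides | 0-5 score for about 600 taxa |

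The reference list does not reconcile them. One cited title treats HOMIM and HOMINGS as two technologies, and the paper cited for the laboratory method is by its title a microarray study. No arithmetic is involved; the descriptions cannot all be true of one assay.

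**Step 2: what ignoring the pairing does.** The plan gives no effect size, SD or power behind its 20 subjects, so there is no figure to reproduce. For equal variances σ² and within-subject correlation ρ, the variance of a paired difference is 2σ²(1 − ρ). An independent-group test works as if it were 2σ². The ratio is 1 − ρ: 0.7, 0.5 and 0.3 at ρ = 0.3, 0.5 and 0.7. The independent-group test therefore overstates the error and rejects too rarely.

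Simulation, with all inputs assumed except n = 20 and the 0.05 level:
- baseline score frequencies for 0 to 5 of 30/15/15/15/15/10%;
- a latent normal shift of 0.6 SD, which gives a mean fall of 0.88 to 0.89 levels;
- 4,000 replicates; two-sided tests.

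| ρ | Signed-rank power | Kruskal-Wallis power | Kruskal-Wallis rejection with no change |
|---|---|---|---|
| 0 | 38.0% | 39.8% | about 4% |
| 0.3 | 46.6% | 37.4% | about 2.5% |
| 0.5 | 57.5% | 36.2% | about 1.5% |
| 0.7 | 76.8% | 34.6% | about 0.1% |

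A separate re-run with new random numbers agreed within about 3 percentage points.

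**Step 3: inhibition against amount sampled (illustration only).** Take four taxa at 40/30/20/10% of the load, with assumed score cut-points. An 80% kill of every taxon and no kill with one fifth of the plaque both multiply each signal by 0.2. The results are therefore identical:
- unscaled scores go from 5,5,5,4 to 4,4,3,3 in both cases;
- scores scaled to the sample total stay at 5,5,5,4 in both cases;
- relative abundance stays at 40/30/20/10% in both cases.

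Across 100 simulated taxa (20 pairs, signed-rank test, one score level per twofold signal, ρ = 0.5), the share of taxa flagged was:

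| Scenario | Scaled to control spots | Scaled to sample total |
|---|---|---|
| No change | 4.8% | 4.6% |
| Half the plaque, no kill | 37.6% | 4.6% |
| 50% kill of all taxa, same plaque | 37.1% | 4.6% |
| 50% kill of all taxa, twice the plaque | 4.6% | 4.9% |

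With control-spot scaling, less plaque looks like a kill. With sample-total scaling, a uniform kill is invisible. For half the plaque and no kill under control-spot scaling, a per-taxon simulation ranges from 8% to 53% as level width runs from twofold to eightfold and ρ from 0.3 to 0.7. For 25% less plaque the range is 5% to 13%. A paired t calculation on an unscaled continuous signal (SD of paired log differences 0.5 to 1.0) gives 84% to 100% for half the plaque. That range does not overlap 8% to 53%, so the assumptions decide the size.

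**The case against.** The assay conflict and the absence of a paired test are hard to contest. The latitude to choose tests by type of variable and distribution only selects among the tests named, and none of those is paired.

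The objections to the third point are stronger.

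- A reader might infer that neither assay can separate inhibition from sampling. The documents do not support that. The HOMINGS section promises concentration levels for each taxon. Normalization is set by a cited paper, and DNA purification follows a modified kit procedure with a cited laboratory web page. Either source could contain a fixed DNA input or a control that this text does not show. The supportable statement is that the documents do not show the separation.
- A reader might also take the simulated rates as the expected share of false findings. They rest wholly on assumed inputs, and no section gives the size or direction of any difference in plaque between visits. Hygiene instruction and a change in lesion hardness make a difference plausible, no more.
- Replacing inhibition with a change in composition is not automatically safe. Under control-spot scaling, half the plaque with unchanged composition still flags about 37% of taxa. That objection stands and limits the wording in the fix.
- The objective and the outcome section are already non-directional. The overreach is confined to the hypothesis and to the phrase about bacteria being arrested.

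A paired test for each taxon also does not settle multiplicity: 0.05 × 600 = 30 flagged taxa would be expected with no effect. That is a separate matter.

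**Conclusion.** Two parts are wrong as written and need correction before analysis. The plan describes two assays and defines an outcome for only one of them; this needs no assumptions. It also names no paired test for a comparison of the same subjects at two visits. It would be a mistake to read this second error as producing false positives: with positively correlated visits the named tests are conservative, and the cost is power. On the assumptions in Step 2 the cost is about 9 percentage points at a correlation of 0.3 (46.6 − 37.4) and about 42 at 0.7 (76.8 − 34.6), with nothing lost at zero.

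The third part is smaller. No sampled amount or DNA input is stated and normalization is given only by citation, so a conclusion of inhibition is not supported by what the documents show. Its size cannot be derived from them. Nor do they settle which assay description is the correct one; only the laboratory can.

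**What to change.** 1. **Assay.** Confirm with the laboratory which assay is run, and use one description throughout. State the matching output variable, DNA input and normalization. If the array is run, keep the 0-5 score and correct the Introduction. If sequencing is run, define a read-count or relative-abundance variable with a named compositional method and a rule for zeros, and delete the fluorescence text.
2. **Tests.** For baseline against one month, replace the independent-group tests with paired ones: signed-rank for 0-5 scores, paired t for continuous measures, McNemar for presence or absence.
3. **Hypothesis.** Restate both hypotheses and the planned conclusion as a change in taxon-level signal between visits. Use change in composition only if the stated variable is scaled to the sample total or is relative abundance. State that the amount sampled is not controlled.

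The cost is one laboratory query, wording changes and named tests. The downside is a weaker conclusion than inhibition, and one of the two assay descriptions, possibly with the 0-5 score, has to be given up. A total-load assay is optional and not required by this fix.
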